## **VII. Inclusion Criteria**

Our subject population is one group of patients who has the diagnosis of systolic heart failure.

Inclusion criteria:

Cardiomyopathy, ischemic or non-ischemic on optimal medical therapy per current heart failure treatment guidelines for at least 3 months.

LVEF <=35% by echocardiogram

Prior implantation of pacemaker/defibrillator with at least atrial and RV mid septal leads. Atrial lead can be waived if RV lead has atrial sensing capabilities.

Presence of right bundle branch block (RBBB), with QRS duration =>120 msec

Normal sinus rhythm

PR interval <250 msec on surface EKG

-Note: Subjects with Biventricular pacemaker/ICD will be enrolled if their LV lead has been deactivated by the their primary cardiologist prior to study enrollment for at least 3 months (this could be due to lead malfunction or the decision to deactivate the biventricular pacing therapy for any reason per primary cardiologist discretion)

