Our study's design is a randomized controlled single blinded cross-over study. Overall designs will include two 12 weeks treatment periods separated by 8 weeks washout periods.

One group will have pacing-washout-placebo sequence while the other will have placebo-washout-pacing sequence. Subjects will be randomized to either pacing (intervention) or non-pacing (placebo) with 1:1 ratio at the initial visit. Each subject will undergo heart ultrasound (echocardiogram), symptoms/quality of life assessment, and 6 minute walking distance assessment at initial, 12, 20, 32 weeks visits. This type of clinical trial design will have an advantage of blinding the intervention to the subject which will minimize bias and would create a control group. Indeed, will allow still to use relatively small number of subjects with enough power to test outcomes comparable to single arm prospective trial design, while parallel randomized controlled studies design would require higher subjects numbers for reaching an adequate power to test outcomes of interest due to lack of self control.

This study will allow us to evaluate the effect of this intervention on heart failure symptoms, heart size and function as well as quality of life in this specific group of heart failure patients.

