## **VI. Main Hypothesis**

To determine whether cardiac resynchronization therapy by single right ventricular lead in heart failure patient with RBBB will be associated with positive reverse left ventricular remodeling and improvement in heart failure symptoms and quality of life.

Primary endpoint Positive reverse left ventricular remodeling, defined as increase in LV Ejection Fraction  $>15\%$  from baseline at 6 months.

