## VIII. Study Procedures

After informative consent signed by potential subject and at the same visit (initial visit), every subject will undergo pacemaker/defibrillator screening check, transthoracic echocardiogram if no echocardiogram available within 6 months preceding the initial visit, and pregnancy test for females whose age 18-50 year-old, if subject is deemed still eligible based on the results of this initial visit screening tests, he/she will be randomized to one of the study's arm and undergo the following baseline tests/procedures.

Initial visit baseline tests/procedures:

A- 6-minute walking test if subject has not had one within 3 months prior to enrollment.

B- Subject will be requested to fill two questionnaires:

- 1- "Minnesota living with heart failure" questionnaire to assess your quality of life
- 2- "Self-assigned New York Heart Association survey (SA-NYHA)" to evaluate the severity of your heart failure symptoms.

C- Medications review, vital signs (heart rate, blood pressure measurement, and weight)

D Baseline pre- and post-programming 12 leads EKG

E- Pacemaker/defibrillator programming session will be performed on all subjects.

Patient assigned to the arm that start with pacing initial treatment period, their devices will be programmed according to our study protocol for RBBB pacing therapy.

After the initial visit, subject will be scheduled for follow up visits. Each visit will last approximately (60-120 minutes) and will be located at University of Iowa Heart and Vascular center –adult outpatient facilities where each subject will have the following tests performed:

A-Follow up trans-thoracic echocardiogram

B-Follow up 6-minute walking test

C-Subject will be requested to fill the two-questionnaire mentioned above again for follow up purposes.

D-Medications review, follow up vital signs (heart rate, blood pressure measurement, and weight)

E-Subject will be asked whether has been hospitalized, has had any medication changes, or has suffered any acute myocardial infarction or stroke/TIA for the preceding 3 months.

F- Blood draw for laboratory tests (Sodium, BUN, Cr, and NT-proBNP)

G-Baseline pre- and post-programming 12 leads EKG

H-Follow up pacemaker/defibrillator check

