Cover Page for Statistical Analysis Plan

Sponsor-Investigator:	[name]
NCT Number:	NCT02441101
Unique Protocol ID:	201409760
Official Title:	Right Ventricular Septal Pacing in Patients With Right Bundle Branch Block and Heart Failure (The SPARK Trial)
Date of Document:	24 December 2014

Linear mixed model analysis for repeated measures will be used to test for change over the follow-up period in the primary outcome measures. Post-hoc pairwise comparison with baseline will be performed using Dunnett's test. Mean estimates at each time point, and mean change from baseline (with 95% confidence limits) will be computed from the fitted model. All tests were two-tailed and a $p < 0.05$ was considered as statistically significant. All analyses will be conducted using the intention-to-treat population.

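### Under Study Procedures the echo that admits a subject at LVEF 35% or below also serves as baseline, which biases changes from baseline upward; the Introduction schedules a separate echo, and the two must be reconciled

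*Protocol*

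**What the plan says.** Protocol section VII admits subjects on "LVEF <=35% by echocardiogram" and asks for no confirmatory reading. Section VIII calls for a "transthoracic echocardiogram if no echocardiogram available within 6 months preceding the initial visit", so an older echo is accepted where one exists. The subject goes on "if subject is deemed still eligible based on the results of this initial visit screening tests", and then "he/she will be randomized to one of the study's arm and undergo the following baseline tests/procedures". That baseline list (items A to E) covers the walk test, questionnaires, medications and vital signs, EKG and device programming. It contains no echo.

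Section I reads differently. It says each subject has an echo along with the symptom and "6 minute walking distance assessment at initial, 12, 20, 32 weeks visits", with no exception for those who already have a recent echo.

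The primary endpoint (section VI) is "defined as increase in LV Ejection Fraction" of more than 15% "from baseline at 6 months". Whether 15% is relative or in absolute points is not said. The SAP tests change over follow-up with a mixed model, and "Post-hoc pairwise comparison with baseline will be performed" by Dunnett's method. It also reports mean changes with 95% limits. It names no treatment, period or sequence term, and neither document says which echo is the baseline.

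**The concern.** An LVEF reading varies from one echo to the next. If subjects enter because one reading fell at or below a cut-off, readings that happened to err low are over-represented. When that same reading is the reference value, later echoes drift back up without any change in the heart. Follow-up at weeks 12, 20 and 32 would then show a mean rise in both sequences, and it would look like the reverse remodeling the trial hopes to find.

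This matters here because every comparison the SAP names is over time or against baseline. Protocol section II says a positive result would support a large multi-center trial, so a selection artefact could carry weight in that decision.

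**Working it through.** **1. Which echo is the baseline?** There are two readings of the protocol.
- Section VIII governs: the only pre-treatment LVEF is the one that decided eligibility, so the overlap covers all subjects.
- Section I governs: a subject who qualified on a pre-study echo has a second, initial-visit echo that can be the baseline, provided the cut-off is not applied to it again. A subject with no echo in the preceding 6 months qualifies on the initial-visit echo itself, so the overlap remains.

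The share of subjects in the second group is not given.

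**2. Inputs.** From the documents: cut-off 35, N = 40, baseline plus three follow-up echoes, two-sided 5%. Not in the documents, and therefore assumed: the mean of true LVEF in the screened population, its between-subject SD (sb) and the echo-to-echo SD within a subject (sw). No dropout and no pacing effect are assumed.

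**3. Nominal level.** Simulating the SAP's analysis as a balanced repeated-measures model (Dunnett critical value 2.385 for three comparisons, 117 df), with no selection on LVEF, gives a chance of any rejection of 0.050. This reproduces the stated 5%.

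**4. Expected spurious rise.** With s = √(sb² + sw²) and a = (35 − mean)/s,

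rise = (sw²/s) × φ(a)/Φ(a).

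Middle case (mean 30, sb 7, sw 5): s = √(49 + 25) = 8.60; a = 5/8.60 = 0.581; φ = 0.337; Φ = 0.720; rise = (25/8.60) × (0.337/0.720) = 1.36 points.

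For scale, the standard error of one change from baseline is about √(2 × 25/40) = 1.12, so the artefact alone is 1.36/1.12 = 1.2 standard errors.

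**5. Results with the qualifying echo as baseline, no pacing effect, N = 40.**

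| Assumed mean, sb, sw | Rise (points) | Any false Dunnett rejection |
|---|---|---|
| 25, 7, 3 | 0.22 | about 6% |
| 28, 6, 4 | 0.66 | about 12% |
| 30, 7, 5 | 1.36 | about 27% |
| 32, 7, 6 | 2.35 | about 52% |

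The largest rise on the grid of means 28 to 32, sb 6 to 8 and sw 4 to 6 is about 2.5 points. These are not bounds. At sb 8 and sw 5, a screened mean of 35 gives 2.1 points and 56% to 58%.

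**6. Separate baseline echo.** With an independent baseline for everyone, the mean change is about 0 and the error about 5%. With a separate baseline for half the subjects, the error is about 5% to 15% for screened means of 25 to 32. At sb 8 and sw 5 it is 6%, 9% and 18% for means of 25, 30 and 35.

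**7. Responder endpoint** (mean 30, sb 8, sw 5). A relative rise above 15% occurs in 36% of subjects, against 30% with a separate baseline. An absolute rise above 15 points occurs in 2.3%, against 1.7%.

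**8. Randomized contrast.** Comparing week 12 with week 32 by sequence gives a rejection rate of 0.045 to 0.053 in every scenario, even with the qualifying echo as baseline.

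**The case against.** A reader might infer that every subject's baseline is the qualifying reading, so that all 40 are affected. The documents do not settle that. Section I schedules an initial-visit echo for each subject, and on that text some subjects already have a second reading. What stands against the plan is the conflict between sections I and VIII, the lack of any definition of baseline, and the overlap that remains under either reading for subjects without a recent echo.

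A reader might also take one of the error rates above as the trial's own. No LVEF mean or SD is in the documents, and with a low screened mean and a precise echo the inflation is slight (6%). Only the upward direction is secure.

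A third inference would be that the pacing effect itself is biased. It is not: both conditions carry the same artefact, and a pacing versus non-pacing contrast removes it. This leads to the best counter-argument, that the real gap is the missing treatment contrast. With 1:1 sequences, weeks 12 and 32 each mix paced and unpaced subjects, so even an unbiased change from baseline would not test pacing. That is correct, and the fix has to include the contrast. It does not excuse the baseline, because the SAP as written reports changes from baseline.

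Finally, most no-effect responders on the relative definition come from measurement noise (30% with a separate baseline). A cleaner baseline removes only the increment to 36%.

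**Conclusion.** The concern holds in limited form. Where the qualifying reading is the baseline, the SAP's changes from baseline and Dunnett tests are biased upward with no pacing effect. This applies to all subjects if section VIII governs, and to those without a recent echo if section I governs.

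The size cannot be known from the documents. Under the assumed values (screened mean 25 to 32, between-subject SD 6 to 8, echo-to-echo SD 3 to 6) the rise is about 0.2 to 2.5 points. The any-Dunnett error in the cases run is about 6% to 52%, falling to about 5% to 15% if half the subjects have a separate baseline. A relative 15% response is moderately inflated and an absolute 15-point response hardly at all. The randomized contrast is unaffected, but the SAP does not specify one. This is a cheap improvement and not a fatal flaw.

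**What to change.** Reconcile Protocol sections I and VIII, and state in both the protocol and the SAP that:
- the qualifying echo is used for eligibility only;
- for subjects who qualify on a pre-study echo, baseline LVEF is the initial-visit echo that section I schedules, and the cut-off is not re-applied to it;
- for subjects whose initial-visit echo is the qualifying one, that LVEF enters the model as a covariate and is not the Dunnett reference;
- any treatment conclusion rests on the within-subject pacing versus non-pacing contrast, with period and sequence terms, and changes from baseline are not interpreted as pacing effects.

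Repeating the acquisition at the same visit is a weaker alternative, because the two readings share that day's variation. If half the within-subject variance were day-to-day (an assumption), about half of the 1.36 points, or 0.68, would remain.

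Cost: a few sentences in each document, plus an echo for subjects with a recent one if section VIII reflects actual practice. Fewer subjects will contribute a change from baseline or a responder status. Their number is unknown, because the share without a pre-study echo is not given. Reported changes from baseline will also be smaller.

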## **Exclusion Criteria**

Age younger than 18 years old

Any other known conditions other than heart failure that could limit survival to < 6 months.

Acute Myocardial infarction within 6 months of entry into the study

Pregnancy

Inotrope dependent heart failure condition

Left ventricular assist device (LVAD) or heart transplantation

Atrial fibrillation or flutter burden >10% within the last 6 months

Atrioventricular node block disease requires ventricular pacemaker support >10% of the time.

## VIII. Study Procedures

After informative consent signed by potential subject and at the same visit (initial visit), every subject will undergo pacemaker/defibrillator screening check, transthoracic echocardiogram if no echocardiogram available within 6 months preceding the initial visit, and pregnancy test for females whose age 18-50 year-old, if subject is deemed still eligible based on the results of this initial visit screening tests, he/she will be randomized to one of the study's arm and undergo the following baseline tests/procedures.

Initial visit baseline tests/procedures:

A- 6-minute walking test if subject has not had one within 3 months prior to enrollment.

B- Subject will be requested to fill two questionnaires:

- 1- "Minnesota living with heart failure" questionnaire to assess your quality of life
- 2- "Self-assigned New York Heart Association survey (SA-NYHA)" to evaluate the severity of your heart failure symptoms.

C- Medications review, vital signs (heart rate, blood pressure measurement, and weight)

D Baseline pre- and post-programming 12 leads EKG

E- Pacemaker/defibrillator programming session will be performed on all subjects.

Patient assigned to the arm that start with pacing initial treatment period, their devices will be programmed according to our study protocol for RBBB pacing therapy.

After the initial visit, subject will be scheduled for follow up visits. Each visit will last approximately (60-120 minutes) and will be located at University of Iowa Heart and Vascular center –adult outpatient facilities where each subject will have the following tests performed:

A-Follow up trans-thoracic echocardiogram

B-Follow up 6-minute walking test

C-Subject will be requested to fill the two-questionnaire mentioned above again for follow up purposes.

D-Medications review, follow up vital signs (heart rate, blood pressure measurement, and weight)

E-Subject will be asked whether has been hospitalized, has had any medication changes, or has suffered any acute myocardial infarction or stroke/TIA for the preceding 3 months.

F- Blood draw for laboratory tests (Sodium, BUN, Cr, and NT-proBNP)

G-Baseline pre- and post-programming 12 leads EKG

H-Follow up pacemaker/defibrillator check

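### The echocardiogram that may serve as the LVEF baseline can be up to 6 months old, which conflicts with the visit schedule and can predate the 3-month therapy and LV-lead requirements

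*Protocol*

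**What the plan says.** The design description in Protocol section I makes no exceptions: "Each subject will undergo heart ultrasound (echocardiogram), symptoms/quality of life assessment, and 6 minute walking distance assessment at initial, 12, 20, 32 weeks visits".

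Section VIII differs. Among the screening steps of the initial visit it lists a "transthoracic echocardiogram if no echocardiogram available within 6 months preceding the initial visit". The baseline tests that follow randomisation (items A to E) are the walk test, questionnaires, medications and vital signs, EKG and device programming; no echo is among them. The walk test is also conditional: a "6-minute walking test if subject has not had one within 3 months prior to enrollment".

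Section VII requires cardiomyopathy "on optimal medical therapy per current heart failure treatment guidelines for at least 3 months". It admits biventricular devices if the "LV lead has been deactivated by the their primary cardiologist prior to study enrollment for at least 3 months". The LVEF criterion of 35% or less carries no date.

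The primary endpoint in section VI is "Positive reverse left ventricular remodeling, defined as increase in LV Ejection Fraction" of more than 15% from baseline at 6 months. The SAP says "Post-hoc pairwise comparison with baseline will be performed using Dunnett's test" and "mean change from baseline (with 95% confidence limits) will be computed from the fitted model". Neither document defines baseline.

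**The concern.** Sections I and VIII cannot both be followed as written. Under section VIII, a subject with an accepted earlier echo has none at entry. The old echo then probably has two uses: it shows that LVEF is 35% or less, and it is the reference for the primary endpoint and the SAP's comparisons.

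Section VII asks for a settled treatment state before entry, but section VIII lets LVEF be measured before that state began. LVEF may change after therapy is optimised or an LV lead is switched off. If so, that earlier change is counted as change during the trial. It can go either way, so the result could be flattered or masked. A subject whose LVEF has since risen above 35% could also be enrolled.

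**Working it through.** The plan states no figure to reproduce: 40 subjects are planned, with no power, effect size or SD. The check is window arithmetic, some algebra, and an illustration on assumed inputs.

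**1. Windows (from the protocol).** Maximum accepted echo age is 6 months (section VIII). Minimum time on optimal therapy, or since LV-lead deactivation, is 3 months (section VII). 6 − 3 = 3, so in a subject who just meets the minimum the echo can predate the change by up to 3 months. The walk test's 3-month window need not predate either requirement, so its only problem is the contradiction with section I.

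**2. Which analyses are affected.** Let B be the baseline LVEF, and Y12 and Y32 the values at the end of each period. In the pacing-first sequence, pacing minus placebo is (Y12 − B) − (Y32 − B) = Y12 − Y32. B cancels, and likewise with signs reversed in the other sequence. B does not cancel from Y12 − B or Y32 − B. Those are the quantities behind the Dunnett comparisons, the mean changes from baseline and the 15% threshold.

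**3. Shift in mean change.** Shift = f × d, where f is the share affected and d the drift in LVEF points since the old echo. Both are assumptions.

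- f = 10%: 0.10 × 3 = 0.3; 0.10 × 5 = 0.5 points
- f = 25%: 0.25 × 3 = 0.75; 0.25 × 5 = 1.25 points

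The sign follows the drift.

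**4. False significance.** Take no pacing effect, n = 40, and a mean shift δ of 1 point (for example 25% × 4). For an unadjusted two-sided 5% comparison with baseline, P = Φ(δ√40/s − 1.96) + Φ(−δ√40/s − 1.96), where s is the SD of change. This gives 0.353 at s = 4 and 0.124 at s = 8, against 0.05 with no drift. Dunnett adjustment would lower these somewhat.

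**5. Responder threshold.** Assume an unpaced subject, baseline LVEF 28 and single-echo SD 4. The SD of a difference is √2 × 4 = 5.66. P(cross) = 1 − Φ((T − d)/5.66), with T = 0.15 × 28 = 4.2 points if the 15% is relative, or T = 15 points if absolute.

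| Drift d | Relative, T = 4.2 | Absolute, T = 15 |
|---|---|---|
| −5 | 5.2% | 0.0% |
| −3 | 10.2% | 0.1% |
| 0 | 22.9% | 0.4% |
| +3 | 41.6% | 1.7% |
| +5 | 55.6% | 3.9% |

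The d = 0 row is measurement error alone, not echo age. The other rows apply only to affected subjects. Trial-wide, the rate is (1 − f) × P(0) + f × P(d). For d from −5 to +5:

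- f = 10%: 21.1% to 26.2% (relative); 0.4% to 0.7% (absolute)
- f = 25%: 18.5% to 31.1% (relative); 0.3% to 1.3% (absolute)

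The no-drift rate depends on the assumed SD. On the relative reading it is 16.1% at SD 3 (4.2/4.24 = 0.99) and 31.0% at SD 6 (4.2/8.49 = 0.495).

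**The case against.** - **The sections can be read together.** The section VIII waiver sits among screening tests, and section I could be taken as requiring a separate baseline echo. List A to E may simply be incomplete, since it also omits the blood tests done at follow-up. This is possible, so the link to the endpoint is inference. But the same list waives the walk test that section I requires of everyone, which suggests that section VIII really does replace initial-visit measurements with earlier ones.
- **Few subjects may be affected.** The echo must be 3 to 6 months old and the therapy change or deactivation must come after it. Anyone stable for 6 months or more is outside the problem, and the LV-lead route concerns biventricular devices only. This stands, and the shares used above are arbitrary.
- **The effect is modest.** At 25% affected, the relative-threshold rate moves from 22.9% by −4.4 to +8.2 percentage points, the latter about 3.3 of 40 subjects. On the absolute reading it moves by less than 1 point. This also stands.
- **The larger defect is the missing treatment contrast.** With a pacing-minus-placebo comparison the mean bias would vanish. That is true, but the SAP names none, and the contrast would not cure the eligibility problem.
- **Fresh echoes exist later.** Week 20 precedes period 2, and in the placebo-first sequence weeks 12 and 20 both precede pacing. However, neither document names these as baseline, and the pacing-first sequence has no such echo before its pacing period.
- **The SAP may not put baseline in the model.** Since mean change from baseline is to come from the fitted model, baseline must enter it in some form.

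**Conclusion.** The concern holds. Two parts are firm: sections I and VIII contradict each other on the initial-visit echo and walk test, and the baseline for the primary endpoint is undefined. The window mismatch of up to 3 months is also firm.

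The bias is conditional on the old echo being used as baseline and on LVEF having changed since. Its size cannot be derived from the documents. Under the assumed 10% to 25% affected and 3 to 5 points of drift, mean changes from baseline are off by 0.3 to 1.25 points in either direction, with a limited effect on the responder rate. Randomisation balances old echoes between sequences in expectation, but that does not remove drift from a comparison with baseline. This should be corrected because it concerns the reference value of the primary endpoint; it is not fatal to the trial.

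**What to change.** Reconcile sections I and VIII of the protocol. Do the echo in every subject at the initial visit, before randomisation and device programming, and state in both protocol and SAP that it is the analysis baseline. Do the walk test at the same visit, for consistency with section I.

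Reconcile the 6-month echo window in section VIII with the 3-month requirements in section VII, so that the LVEF used for eligibility reflects the same treatment state as the baseline. Older echoes can still serve for pre-screening.

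The cost is at most one echo and one walk test for each subject who already has a recent one, at a visit already held and already described that way in section I. A few pre-screened subjects may fail on the repeat echo, slowing recruitment slightly in a 40-subject trial.

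This removes the echo-age problem only. Regression to the mean remains if one echo both confirms eligibility and serves as baseline.
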